## **8.0 ADVERSE EVENTS: LIST AND REPORTING REQUIREMENTS**

The following is a list of AEs (Section 8.1) and the reporting requirements associated with observed AEs (Sections 8.3 and 8.4).

The clinical course of each event will be followed until resolution, stabilization, or until it has been determined that the study treatment or participation is not the cause. Serious adverse events that are still ongoing at the end of the study period will necessitate follow-up to determine the final outcome. Any serious adverse event that occurs after the study period and is considered to be possibly related to the study treatment or study participation will be recorded and reported immediately.

### **8.1 Adverse Events and Potential Risks**

#### **8.1.1 *LevulanTM***

ALA is a natural component found in all cells in the human body. The application of ALA mixed in an alcohol-based vehicle (Kerastick) is not associated with any risks or side effects.

#### **8.1.2 *Photodynamic Therapy***

When ALA is converted into PpIX in tumor cells, and illuminated with light, the following signs and symptoms are known to occur as part of the therapeutic response:

- (i) Stinging and/or burning sensation: >50%
- (ii) Erythema (localized redness): 35%
- (iii) Edema, localized: >35%
- (iv) Peeling, transient: <50%
- (v) Blister formation: rare

#### **8.1.3 *Photodynamic Therapy response (with local cutaneous effects):***

The constellation of transient local symptoms of stinging and/or burning, itching, erythema and edema as a result of LEVULAN KERASTICK Topical Solution plus BLU-U treatment was observed in all clinical studies of LEVULAN KERASTICK for Topical Solution Photodynamic Therapy for actinic keratoses treatment. Stinging and/or burning subsided between 1 minute and 24 hours after the BLU-U Blue Light Photodynamic Therapy Illuminator was turned off, and appeared qualitatively similar to that perceived by patients with erythropoietic protoporphyria upon exposure to sunlight. There was no clear drug dose or light dose dependent change in the incidence or severity of stinging and/or burning.

#### **8.1.4 *Extra-cutaneous adverse experiences reported:***

In Phase 3 studies, no non-cutaneous adverse events were found to be consistently associated with LEVULAN KERASTICK Topical Solution application followed by blue light exposure. No clinically significant patterns of clinical laboratory changes were observed for standard serum chemical or hematologic parameters in any of the controlled clinical trials.

#### **8.1.5 *Safety in pregnancy:***

No carcinogenicity testing has been carried out using ALA. No evidence of mutagenic effects was seen in four studies conducted with ALA to evaluate this potential. No assessment of effects of ALA HCl on fertility has been performed in laboratory animals. It is unknown what effects

systemic exposure to ALA HCl might have on fertility or reproductive function. Therefore, Levulan is considered as Pregnancy Category C.

## 8.2 Definitions

### 8.2.1 *Adverse Events*

An **adverse event** (AE) is any unfavorable or unintended event, physical or psychological, associated with a research study, which causes harm or injury to a research participant as a result of the participant's involvement in a research study. The event can include abnormal laboratory findings, symptoms, or disease associated with the research study. The event does not necessarily have to have a causal relationship with the research, any risk associated with the research, the research intervention, or the research assessments.

Adverse events may be the result of the interventions and interactions used in the research; the collection of identifiable private information in the research; an underlying disease, disorder, or condition of the subject; and/or other circumstances unrelated to the research or any underlying disease, disorder, or condition of the subject. In general, adverse events that are at least partially the result of (a) or (b) would be considered related to the research, whereas adverse events solely related to (c) or (d) would be considered unrelated to the research.

**External adverse events** are adverse events experienced by subjects enrolled in multicenter clinical trials at sites other than the site(s) over which the Institutional Review Board has jurisdiction.

**Internal adverse events** are adverse events experienced by subjects enrolled at the site(s) under the IRB's jurisdiction for either multicenter or single-center research projects.

8.2.2 **The significance of an adverse event** is used to describe the patient/event outcome or action criteria associated with events that pose a threat to a patient's life or functioning (i.e., moderate, severe or life threatening). Based on the National Cancer Institute Guidelines for the Cancer Therapy Evaluation Program, severity can be defined by the following grades of events:

**Grades 1** are mild adverse events. (e.g., minor event requiring no specific medical intervention; asymptomatic laboratory findings only; marginal clinical relevance)

**Grades 2** are moderate adverse events (e.g., minimal intervention; local intervention; non-invasive intervention; transfusion; elective interventional radiological procedure; therapeutic endoscopy or operation).

**Grades 3** are severe and undesirable adverse events (e.g., significant symptoms requiring hospitalization or invasive intervention; transfusion; elective interventional radiological procedure; therapeutic endoscopy or operation).

**Grades 4** are life threatening or disabling adverse events (e.g., complicated by acute, life-threatening metabolic or cardiovascular complications such as circulatory failure, hemorrhage, sepsis; life-threatening physiologic consequences; need for intensive care or emergent invasive procedure; emergent interventional radiological procedure, therapeutic endoscopy or operation).

**Grades 5** are fatal adverse events resulting in death.

### 8.2.3 *Serious Adverse Events*

A *serious adverse event* (SAE) is any adverse experience occurring at any dose that results in any of the following outcomes:

- Results in *death*.
- Is a *life-threatening* adverse experience. The term life-threatening in the definition of serious refers to an adverse event in which the subject was at risk of death at the time of the event. It does not refer to an adverse event which hypothetically might have caused death if it were more severe.
- Requires *inpatient hospitalization or prolongation of existing hospitalization*. Any adverse event leading to hospitalization or prolongation of hospitalization will be considered as Serious, UNLESS at least one of the following expectations is met:
  - The admission results in a hospital stay of less than 12 hours OR
  - The admission is pre-planned (i.e., elective or scheduled surgery arranged prior to the start of the study) OR
  - The admission is not associated with an adverse event (e.g., social hospitalization for purposes of respite care).

However it should be noted that invasive treatment during any hospitalization may fulfill the criteria of “medically important” and as such may be reportable as a serious adverse event dependant on clinical judgment. In addition where local regulatory authorities specifically require a more stringent definition, the local regulation takes precedent.

- Results in *persistent or significant disability/incapacity*. The definition of disability is a substantial disruption of a person’s ability to conduct normal life’s functions.
- Is a *congenital anomaly/birth defect*.
- Is an *important medical event*. Important medical events that may not result death, be life-threatening, or require hospitalization may be considered a serious adverse experience when, based upon appropriate medical judgment, they may jeopardize the patient or subject and may require medical or surgical intervention to prevent one of the outcomes listed in this definition. Examples of such medical events include allergic bronchospasm requiring intensive treatment in an emergency room or at home, blood disease or disorders, or convulsions that do not result in inpatient hospitalization, or the development of drug dependency or drug abuse.

### 8.2.4 *Expectedness*

Adverse Events can be Expected or Unexpected.

*An expected adverse event* is an event previously known or anticipated to result from participation in the research study or any underlying disease, disorder, or condition of the subject. The event is usually listed in the Investigator Brochure, consent form or research protocol.

*An unexpected adverse event* is an adverse event not previously known or anticipated to result from the research study or any underlying disease, disorder, or condition of the subject.

### 8.2.5 *Attribution*

Attribution is the relationship between an adverse event or serious adverse event and the study drug. Attribution will be assigned as follows:

- Definite – The AE is clearly related to the study drug.
- Probable – The AE is likely related to the study drug.
- Possible – The AE may be related to the study drug.
- Unlikely – The AE is doubtfully related to the study drug.
- Unrelated – The AE is clearly NOT related to the study drug.

### **8.3 Reporting Procedures for All Adverse Events**

*This section is not yet determined, pending the outcome of our application to the FDA.*

All participating investigators will assess the occurrence of AEs throughout the subject's participation in the study. The clinical course of each event will be followed until resolution, stabilization, or until it has been determined that the study treatment or participation is not the cause.

The investigator is responsible for ensuring that all adverse events observed by the investigator or reported by the subject which occur after the subject has signed the informed consent are fully recorded in the subject's case report form, subject's medical records, and/or any other institutional requirement. Source documentation must be available to support all adverse events.

A laboratory test abnormality considered clinically relevant (e.g., causing the subject to withdraw from the study), requiring treatment or causing apparent clinical manifestations, or judged relevant by the investigator, should be reported as an adverse event.

The investigator will provide the following for all adverse events:

- Description of the event
- Date of onset and resolution
- Grade of toxicity
- Attribution of relatedness to the investigational agent
- Action taken as a result of the event
- Outcome of event

In this study, descriptions and grading scales found in the NCI Common Terminology Criteria for Adverse Events (CTCAE) version 4.0 available at <http://ctep.cancer.gov> will be utilized for AE reporting.

Investigative sites will report adverse events to their respective IRB according to the local IRB's policies and procedures in reporting adverse events.

### **8.4 Serious Adverse Event Reporting Procedures**

*This section may need revision if Sponsor or Funding Source of study has specific reporting requirements for trial, and/or if study is conducted under an IND.*

Serious adverse events that occur beginning with the signing of the informed consent, during treatment, or within 30 days of the last dose of treatment must be reported to the CCF Principal Investigator.

Investigative sites will report serious adverse events to their respective IRB according to the local IRB's policies and procedures in reporting serious adverse events.

**8.4.1 Pharmaceutical Sponsor Reporting: N/A**

**8.4.2 FDA Reporting: N/A**

**8.5 Data Safety Toxicity Committee**

It is the Case Comprehensive Cancer Center's Principal Investigator's responsibility to ensure that ALL serious adverse events are reported to the Case Comprehensive Cancer Center's Data Safety Toxicity Committee. This submission is simultaneous with their submission to the Sponsor or other Regulatory body.

## 9.0 PHARMACEUTICAL INFORMATION

A list of the adverse events and potential risks associated with the commercial agents administered in this study can be found in Section 8.0.

[figure not shown]
9.1. LevulanTM The following information about LevulanTM is cited from the package insert:

**Chemical Name:** 5-aminolevulinic acid (ALA)

**Other Names:** *delta*-aminolevulinic acid

**Classification:** Topical agent

**Molecular Formula:** The chemical name for ALA HCl is 5-amino-4-oxopentanoic acid hydrochloride (MW = 167.59). The structural formula is represented below:

**Mode of Action:** Photosensitization following application of LEVULAN KERASTICK Topical Solution occurs through the metabolic conversion of aminolevulinic acid to protoporphyrin IX (PpIX), a photosensitizer, which accumulates in the skin to which LEVULAN KERASTICK Topical Solution has been applied. The absorption of light results in an excited state of porphyrin molecules, and subsequent spin transfer from photoreactive porphyrins to molecular oxygen generates singlet oxygen, which can further react to form superoxide and hydroxyl radicals.

**Metabolism:** ALA is converted to PpIX within mitochondria. PpIX is then destroyed upon illumination with the incident light (see above).

**Product description:** LEVULAN® KERASTICK® (aminolevulinic acid HCl) for Topical Solution, 20%, a porphyrin precursor, contains the hydrochloride salt of aminolevulinic acid (ALA), an endogenous 5-carbon aminoketone. The LEVULAN KERASTICK for Topical Solution applicator is a two component system consisting of a plastic tube containing two sealed glass ampules and an applicator tip. One ampule contains 1.5 mL of solution vehicle comprising alcohol USP (ethanol content = 48% v/v), water, laureth-4, isopropyl alcohol, and polyethylene glycol. The other ampule contains 354 mg of ALA HCl as a dry solid. The applicator tube is enclosed in a protective cardboard sleeve and cap.

**Solution preparation:** The 20% topical solution is prepared just prior to the time of use by breaking the ampules and mixing the contents by shaking the LEVULAN KERASTICK applicator. The term “ALA HCl” refers to unformulated active ingredient, “LEVULAN KERASTICK for Topical Solution” refers to the drug product in its unmixed state, “LEVULAN

KERASTICK Topical Solution” refers to mixed drug product (in the applicator tube or after application), and “LEVULAN KERASTICK” refers to the applicator only.

**Storage requirements:** Levulan should be stored at room temperature, 20°-25 °C (68°-77 °F).

**Stability:** The ALA medication in a LEVULAN KERASTICK is stable for over 2 years, if unmixed. After mixing, the LEVULAN KERASTICK Topical Solution should be used immediately following preparation (dissolution). Solution application must be completed within 2 hours of preparation. An applicator that has been prepared must be discarded 2 hours after mixing (dissolving).

**Route of administration:** Levulan™ Kerastick will be applied to the skin, as directed by the manufacturer. Specifically, the glass ampules within the Kerastick will be crushed; the Kerastick shaken for 2 min to allow the powder to adequately dissolve in the vehicle; the liquid applied to the selected areas of skin using foam-tip applicator at the end of the Kerastick, and allowed to air dry for at least 3 min. The study subject will be advised to avoid sunlight until he/she will return to the clinic for the illumination phase of the treatment.

**Drug Procurement:** Levulan™ Kerastick will be purchased from Sun Pharmaceuticals.

**Drug Accountability:** The investigator or designated study personnel are responsible for maintaining accurate dispensing records of the study drug. All study drugs must be accounted for, including study drug accidentally or deliberately destroyed. Under no circumstances will the investigator allow the investigational drug to be used other than as directed by the protocol. If appropriate, drug storage, drug dispensing, and drug accountability may be delegated to the pharmacy section of the investigative site.

**Drug Destruction:** Levulan Kerastick™ can be used only once after mixing. Immediately after application to the patient's skin, the remaining Kerastick will be discarded.

### 9.2. **Cholecalciferol (Vitamin D3 supplements)**

While D3 is not a drug, we describe it here to clarify its source and handling. A large batch of D3 tablets, 10,000 IU per tablet, will be purchased from a commercial source (e.g., NatureMade from Costco, Inc.) and several tables will be sent for testing at a commercial analysis facility to verify the cholecalciferol content (Heartland Assays, Ames, Iowa). These tablets will be stored in the CCF Research Pharmacy, under temperature-controlled conditions.

[NOTE: The CCF Research Pharmacy, under guidance of [name] RPh, will also create inert pills made of inert methylcellulose for use as placebo in this randomized study].

### 9.3. **Light Sources for PDT**

#### **Blue light source: (Blu-U):**

This lamp is FDA-approved, and used routinely in our dermatology clinics.

#### **Noninvasive Fluorescent Measurement Device (NIR):**

This custom-made fluorescent detector, consisting of a safe, low-energy HeNe laser (equivalent to a classroom pointer) and an optical detector to collect weak red fluorescence, was IRB-approved and routinely used in our CCF IRB protocol, 09-1050.

## 10.0 CORRELATIVE / SPECIAL STUDIES

### 10.1 *Processing of blood for serum 25-hydroxy-vitamin D3 measurements.*

#### **Rationale:**

Here we will address the question of whether a patient's overall vitamin D status (as measured by 25OH-D3 serum levels) can affect PpIX production within skin tumors, and the subsequent clinical response to PDT. A large proportion of people in northern climates are VD deficient, especially in winter, as diagnosed by low serum 25OH-D3 levels [35, 36]. There is high variability in the results of different studies, due to multiple factors including sunlight/season, age, ethnicity, and laboratory technique, and to the endpoints being used (bone loss; PTH levels, etc.). Thus, controversy exists about how to define low VitD levels using terms such as "deficiency", "insufficiency", etc. However, most authorities agree that a 25OH-D3 level above 20 ng/mL is required for normal health, with the range of 20 – 60 ng/mL being acceptable to avoid VitD toxicity [35, 36]. In our study, we will use 20 ng/mL as our threshold to define normal Vit D levels. Patients with a suboptimal level (below 20 ng/mL) will be classified into two groups, either moderately deficient (10-19 ng/mL), or severely deficient (<10 ng/mL) for analytical purposes. Thus, the patients' 25OH-D3 levels will be grouped in tertiles (severely deficient, moderately deficient, or optimal) when interpreting the relationship between VitD level and PDT treatment response.

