### **1.5 Preliminary data in mice, supporting the idea that VD status affects PDT outcomes and that neoadjuvant VD effectively boosts PpIX levels in precancerous and cancerous lesions**

Our clinical studies are based upon the [name] laboratory's preclinical work over the last decade [4], showing that epithelial tumors are more responsive to ALA-based PDT when "primed" by pre-exposure to VitD. Cancer cells in culture[15] and NMSC tumors in mice[8] were shown to produce more PpIX and more photoactivation (tumor cell killing) if first exposed for ~3 d to calcitriol. Our enthusiasm for this approach was temporarily dampened because calcitriol, if overdosed, can induce hypercalcemia. However, we have now shown that D3 (the natural dietary form of VitD, which carries little to no hypercalcemic risk) can selectively elevate PpIX levels in murine NMSC tumors as efficiently as systemic calcitriol [12]. Based upon these preliminary data, clinical studies in the current proposal are designed to test the hypothesis that oral D3 supplements, administered over a relatively short time, can boost the effectiveness of ALA-PDT for NMSC in human patients. In mice, we have now shown that D3 (the natural dietary form of VD, which carries little to no hypercalcemic risk) can selectively elevate PpIX levels in murine skin tumors as efficiently as systemic calcitriol [12]. Based upon these preliminary data, clinical studies in the current proposal are designed to test the hypothesis that oral D3 supplements, administered over a relatively short time, can boost the effectiveness of ALA-PDT for NMSC in human patients. In addition, because the majority of people in the U.S. are VD deficient, we will

assess whether or not a patient's VD status (deficient, normal, or replete) can predict therapeutic responsiveness to ALA-PDT.

It has long been thought that VD may be beneficial for suppressing carcinogenesis, an important factor in the development of precancerous and cancerous lesions. For example, in an oral carcinogenesis protocol, VD receptor (VDR) knockout mice developed more BCC than their wild type littermates [16]. BCNS patients tend to be VD deficient, which may hasten BCC development [17]. BCC tumor cells harbor the VDR [18, 19]. The latter fact may be useful if using VD to stimulate PpIX production requires the VDR (which we hope to partially validate by collecting patients' leukocyte DNA and examining VDR gene sequences directly).

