## **14.0 STATISTICAL CONSIDERATIONS**

### **Primary objective:**

#### **Statistical Analysis**

Patients receiving neoadjuvant D3/PDT will be first matched to control patients who received PDT alone (in our previous study, IRB 16-1615) in a 1:1 ratio based upon the baseline 25OH-D3 values. The 25OH-D3 values will have three strata: normal blood levels, intermediate, and low. The matching will also be stratified, i.e., normal level patients who received D3/PDT will be matched to normal level patients who received PDT, and so on. Within each stratum, the matching will be done with the optimal algorithm by considering 25OH-D3 as a continuous variable. The outcome,  $\Delta C$ , (% decrease in lesion number), will then be compared between the two matched groups using the paired t-test. Statistical significance will be established at a two-sided p-value  $< 0.05$ . As a sensitivity analysis, a linear mixed-effect model will be used to adjust the comparison for baseline 25OH-D3 values. A random two-way ANOVA model will also be used to include therapy, D3 strata and their interactions in the model to examine whether the treatment effect differs by strata.

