#### **Secondary objectives:**

- To assess the level of PpIX accumulation in AK lesions at treatment visits, in the absence or presence of neoadjuvant D3. (fluorescence dosimetry measurements)
- To assess tolerability of the technique. (Pain scale measurements)
- To assess patient satisfaction with the technique. (Cosmetic result, and questionnaire)
- To assess D3 serum levels (in serum) and VDR status (in leukocyte DNA), and to correlate these results to clinical outcomes.

Characteristics of the above parameters will be summarized as means and standard deviations (medians and quartiles) or percentages and frequencies. We will also compare the characteristics of screened and randomized patients using appropriate two-sample comparison procedures (t-test, Chi-squared test, etc.).

Analyses of study endpoints will follow the intention-to-treat (ITT) principle. For each relevant

endpoint, we will summarize its trajectories over study visits by randomization assignment for each patient. Linear mixed-effects models will be the primary analytic tools to analyze continuous endpoints by accounting for within-patient randomization, multiple lesions from the same patient and repeated measurements over time. The models will include fixed effects of treatment and visit and multiple random effects that represent the hierarchical data structure. Similarly, generalized linear mixed-effects models will be applied to categorical endpoints (binomial data, e.g., number of lesions with CR). The analysis for time to clearance will be based on a random-frailty survival model, where lesions without CR will be considered to have clearance times censored at the end of study. Further exploratory analyses will adjust these models by controlling for important initial parameters (e.g., initial tumor size).

All analyses will be conducted using SAS 9.3 (Cary, NC). Results will not be adjusted for multiple comparisons, and statistical significance will be established with a two-sided p-value < 0.05.

**Estimate of the accrual rate:** Patients who have been scheduled to receive PDT in our noninvasive cutaneous oncology clinics will be given written information prior to their visit, including a copy of the Informed Consent (IC) that describes the purpose of the study. If the patient indicates that he/she is interested, the physician or study nurse will review the IC with the patient on the day of PDT and answer all questions. We estimate an enrollment of 1 patient each week.

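### The relation of vitamin D level to PDT response is to be read from three fixed classes mislabelled as tertiles; the continuous 25OH-D3 value should be the main analysis

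*Combined protocol and SAP*

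**What the plan says.** Section 10.1 (Rationale) sets the boundary of normal: "In our study, we will use 20 ng/mL as our threshold to define normal Vit D levels". Patients below it are split as "either moderately deficient (10-19 ng/mL), or severely deficient (<10 ng/mL) for analytical purposes". It then says how the classes will be used: "25OH-D3 levels will be grouped in tertiles (severely deficient, moderately deficient, or optimal) when interpreting the relationship between VitD level and PDT treatment response". This is the only scale that the documents name for the level-response question.

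Section 14.0 deals with the level in two places:

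- Under the primary objective, "The 25OH-D3 values will have three strata: normal blood levels, intermediate, and low", with no cut-points given. Within each stratum the matching treats 25OH-D3 as continuous. A sensitivity model adjusts the treatment comparison for baseline 25OH-D3, and a two-way ANOVA tests therapy by stratum.
- Under the secondary objectives, serum levels and VDR status are to be assessed "and to correlate these results to clinical outcomes". No scale or model is named.

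Section 1.5 states the intention to "assess whether or not a patient's VD status (deficient, normal, or replete) can predict therapeutic responsiveness to ALA-PDT", which is a third set of labels. The legend to Figure 5 (Section 3.1) ties the length of the D3 course to normal or deficient status, so in treated patients the course changes at the same 20 ng/mL boundary.

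**The concern.** Classes cut at fixed clinical thresholds are not tertiles. Read literally, *tertiles* asks a programmer for three equal groups of 10 out of 30. The cut-points ask for whatever falls below 10, between 10 and 20, and at or above 20 ng/mL. These are different analyses.

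The larger matter is the scale. Every patient has a measured 25OH-D3 value, and the plan already uses it as a continuous variable for matching. For the question of whether vitamin D status predicts response, however, the only named approach reduces that value to three categories. If the relation is roughly linear, that gives up precision at no saving. The lowest class may also be too small to describe. At stake is a secondary, correlative question, but one that the trial's rationale treats as important.

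**Working it through.** **1. The plan's own figure.** Section 14.0 gives a power calculation for the primary paired comparison only: difference 90 − 70 = 20 points, SD 24, correlation 0.1, two-sided alpha 0.05.

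- SD of a paired difference = 24 × √(2 × (1 − 0.1)) = 32.2.
- Noncentrality at n=30 = 20 × √30 / 32.2 = 3.40.
- Power from the noncentral t distribution = 0.908.

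The stated n=30 for 90% power reproduces. There is no corresponding figure for the level-response analysis.

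**2. What the documents say about the distribution.** They are qualitative only: "A large proportion of people in northern climates are VD deficient, especially in winter" in Section 10.1, and a similar general remark in Section 1.5. No mean, SD or share below 10 ng/mL is given, so everything below rests on assumed distributions.

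**3. Information kept by the classes.** For a linear relation, the share kept is the between-class share of the variance of 25OH-D3:

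K = Σ pₖ(mₖ − m)² / Var(x),

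where pₖ and mₖ are the class proportions and means. I assume a normal distribution truncated at 4 ng/mL, with cuts at 10 and 20.

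| Assumed mean / SD | <10 | 10 to <20 | ≥20 | Expected <10, of 30 | K |
|---|---|---|---|---|---|
| 18 / 8 | 12.4% | 45.8% | 41.8% | 3.7 | 0.77 |
| 28 / 10 | 2.8% | 17.7% | 79.5% | 0.8 | 0.505 |
| 32 / 11 | 1.7% | 11.6% | 86.7% | 0.5 | 0.40 |

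First row in full: class means 7.5, 15.4 and 25.7; overall mean 18.7 and SD 7.3 after truncation. K = [0.124 × 11.2² + 0.458 × 3.3² + 0.418 × 7.0²] / 7.3² ≈ 0.77.

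For reference, true tertiles of a normal variable keep (2/3) × 1.09² = 0.79.

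**4. Power.** Assume a true correlation of 0.45, so R² = 0.2025 on the continuous scale and K × 0.2025 on the classes. Noncentrality is λ = nR²/(1 − R²), referred to the noncentral F distribution. For example, at n=30 the continuous analysis has λ = 30 × 0.2025/0.7975 = 7.6. The 18/8 classes have R² = 0.156 and λ = 5.5.

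| | Continuous, 1 df | Trend over classes, 1 df | Three-group test, 2 df |
|---|---|---|---|
| n=30 | 76% | 62% to 35% | 50% to 26% |
| n=60 | 97% | 91% to 62% | 84% to 50% |

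Ranges run from mean/SD 18/8 to 32/11. The trend test scores each class at its mean. The n=60 row pools treated patients and matched controls, treats them as independent and assumes one common slope. The figures carry no terms for therapy, interaction or D3 course, all of which would reduce power.

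**5. Sensitivity to the assumed shape.** Lognormal shapes, and normals truncated at 2 ng/mL, with mean 20 to 35 and SD 8 to 12 keep 74% down to 15% of the information and put 2.8 down to 0.0 of 30 patients below 10 ng/mL. In the other direction, if 20% of patients were below 10 ng/mL, that class would hold 0.20 × 30 = 6.

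**6. What a small class can show.** With the plan's SD of 24 and 27 residual df (t = 2.05), the 95% interval for mean clearance in a class of 3 is ±2.05 × 24/√3 ≈ ±28 points. That is wider than the 20-point effect planned for. In a class of 10 it is about ±16.

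**The case against.** The best defence has five parts.

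- **A continuous analysis is not excluded.** Section 14.0 says *correlate* and does not confine this to classes. That is correct, so a reader who infers that the plan forbids a continuous analysis goes too far. But the only scale named for this question is the grouping, so the continuous analysis is possible rather than planned.
- **The loss is not established.** A reader might infer that the lowest class will hold almost nobody, or that most of the information goes. The documents support neither as fact, because they give no distribution. At the low end of the assumed range the classes do almost as well as true tertiles (77% against 79%).
- **Part of the power gap comes from the test.** The plan names no three-group test for this relation. Setting a 1-df continuous test against a 2-df comparison mixes two effects, so the trend column is the fair comparison. Including controls, which Section 10.2 implies for the biomarker analyses, raises power on every scale. Both points stand and are shown in the working.
- **The 20 ng/mL boundary is not arbitrary.** In treated patients the D3 course changes there, so a single straight line mixes level with course length. This stands and changes the remedy. If response truly stepped at 10 or 20 ng/mL, grouping would also lose less.
- **The labelling differences are minor.** The three strata in Section 14.0 map in order onto the classes in Section 10.1, and the labels in Section 1.5 are background wording. A value of 19.5 is below 20 and not below 10, so it is moderately deficient by elimination. Inferring three incompatible definitions or an unassigned gap would overstate this.

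**Conclusion.** The point holds in a limited form. The word *tertiles* is wrong for classes cut at 10 and 20 ng/mL. Grouping is the only stated scale for a question that the collected continuous values can answer better if the relation is roughly linear.

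The size depends on a distribution and a correlation that are not in the documents. Under the truncated-normal assumptions the classes keep about 77% to 40% of the linear information. At r=0.45, a fair 1-df comparison costs roughly 14 to 41 percentage points of power at n=30 (76 − 62; 76 − 35) and 6 to 35 at n=60 (97 − 91; 97 − 62). A step-shaped relation would shrink the loss.

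This concerns a secondary analysis only. It would be wrong to infer that the primary paired comparison is underpowered on this account: its n=30 reproduces and does not depend on the class scale of the level-response analysis.

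**What to change.** In Sections 10.1 and 14.0:

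1. Name continuous 25OH-D3 (linear, with one check for curvature) as the main level-response analysis.
2. Fit it in the PDT-alone controls and the treated group together, with a therapy term and a therapy-by-level interaction.
3. In treated patients, add an indicator for the D3 course received, or state that level and course length cannot be separated there.
4. Keep the three classes for description only, with the count in each.
5. Delete *tertiles* and write the same explicit boundaries in both sections: <10, 10 to <20, and ≥20 ng/mL.

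The cost is a few sentences and no new data. The downside is one or two more model terms in a small secondary analysis. With the course indicator, the slope in treated patients rests on variation within each course, so it will be less precise than the simple figures above suggest. The controls, who took no D3, give the cleanest estimate of the relation with level.
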